Primary objective: To determine if combined treatment with dapagliflozin and metformin is more effective than monotherapy with metformin for weight loss and assess its effects on waist circumference, triglycerides, blood pressure and inflammatory cytokines (resistin, adiponectin, interleukin-6 and interleukin-10) in prediabetic and diabetic patients with obesity class III.

Secondary objective: To determine the effect of combined treatment with dapagliflozin and metformin in comparison with monotherapy with metformin on serum concentrations of glucagon, ghrelin and insulin.

Patients, material and methods: The protocol includes patients with previous or recently diagnosed diabetes or prediabetes from the Obesity Clinic of CMN SXXI from July 2018 to August 2023 age 18 to 60 years old, both male or female and not treated with insulin. Patients requiring initial treatment with insulin, with obesity secondary to other comorbidities and patients who do not wish to enter the study or not provide their informed consent will be excluded. Patient's data that during the study are advised to undergo bariatric surgery will be used until the moment of surgery. Other treatments will be adequately recorded. Patients will be randomized by computer software and assigned in a group treated with metformin (>2 g/day, group 1) or with metformin (>2 g/day) and dapagliflozin 10 mg (group 2). All patients will receive dietary treatment and follow-up by the Nutrition service during the study. Anthropometric and biochemical variables will be recorded at the beginning and at months 3, 6 and 12. Adherence to treatment will be assessed, defined by consumption of at least 90% of provided pills. The adverse events will be recorded since the beginning of study and will be ranked according to the CTCAE lists (Common terminology criteria for adverse events version 4.03). An intention-to-treat analysis will be performed in case of patients that require treatment with insulin.

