Santo et al. in 2014 conducted a prospective study for evaluating possible benefits related to pre-surgical weight decrease in patients with super-obesity. In this study, 20 patients had in-hospital strict dietary control with diets between 600 and 1500 kcal plus aerobic physical activity (in those allowed to do it). Patients obtained a reduction of 19.7% of initial weight, with decrease of BMI

from 67 kg/m² to 55 kg/m² over a 24-weeks period. In this group, they observed a lower incidence of complications and decreased time of hospitalization [11].

Prevalence of comorbidities in the Obesity Clinic

The Obesity Clinic evaluates a population of approximately 400 patients, 150 patients have undergone bariatric surgery, 250 patients are pending of approval for such proceedings and up to 10 new patients per month are assessed for determine its possible admission to the clinic.

Sanchez-Ruiz et al. previously performed a retrospective study with a sample of 109 patients from the Obesity Clinic who underwent bariatric surgery between January 2009 and December 2011 (in press). In this study, the mean age was 45.3 ± 10.1 years, 70% were female, 85% reported attachment to diet (up to 80%), 31% performed physical activity (defined as at least 30 minutes of daily walking), 21% were smokers, 74% had a family history of obesity and 67% reported overweight or obesity since childhood. In this study, we observed that 46% of patients had prediabetes (defined by the American Diabetes Association, [ADA] as a plasmatic fasting level greater than 100 mg/dl and less than 126 mg/dl or a 2-h plasma glucose level measured after a 75-g oral glucose load, greater than 140 mg/dl and less than 200 mg/dl) or T2D (defined as fasting glucose greater than 126 mg/dl or a glucose level post-load greater than 200 mg/dl) [12], 66% had HTN and 33% had dyslipidemia (hypertriglyceridemia, hypoalphalipoproteinemia, or both). At this clinic, patients with prediabetes or T2D are usually treated with metformin 2 g/day or Neutral Protamine Hagedorn insulin (NPH) with calculated doses of 0.5 to 1 U/kg of weight when necessary and are evaluated every three months for treatment adjustment depending on their glycated hemoglobin as stipulated by ADA guidelines [12].

Pharmacological treatment of obesity

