Different studies have reported a modest decrease in weight or stability compared with other hypoglycemic medications [46]. Hermann et al. were the first to describe the body weight effects of metformin [47]. In 1991 they studied 25 patients with a mean age of 59 years (range 36-69 years) with an average weight of 76.4 kg (63-97 kg) for women and 77.4 kg (64.5-92 kg) for men previously treated with glyburide. In this group, they observed a decrease of -2.64 kg of total weight (95% CI -4.23 to -1.05 kg) after one year of treatment. Subsequently Stumvoll et al. conducted a study with 10 patients with T2D (6 men and 4 women), aged 58 ± 9 years and average BMI of 32.1 ± 3.2 kg/m² to those treated with initial doses of metformin 850 mg increments every two weeks to 2550 mg (850 mg three times a day) [48]. After 16 weeks observed a total weight loss of -2.7 ± 1.3 kg (95.1 ± 14.9 vs. initial 92.4 ± 14.5 kg end, $p < 0.001$) and -2.4 ± 2.2 kg of fat mass, determined by bioimpedance (initial 31.2 ± 11.4 vs. 28.9 ± 10.1 kg end, $p = 0.02$) [48]. That same year, DeFronzo et al. conducted a study to compare the metabolic effects of metformin, glyburide, and the combination of both. In that study the group with metformin (n=210 patients, average age 55 ± 1 years, mean BMI 29.4 ± 0.3 kg/m²) reported a loss of -3.8 ± 0.2 kg, compared with less weight loss observed in the group with glyburide or the weight gain observed in the group with combination therapy for 29 weeks [49].

Moreover, Mogul et al. conducted a retrospective analysis of 30 non-diabetic women who previously tried to lose weight with diet and exercise and grouped them into two categories of BMI: 25 to 32.9 kg/m² (group 1) and 33 to 41.7 kg/m² (group 2). In addition to a hypocaloric diet, they received a dose of 1500 mg and 2000 mg metformin, respectively. In group 1, a loss of 3.47 kg (SE, standard error 0.68), 6.41 kg (0.72) and 8.06 kg (0.96) at 3, 6 and 12 months of treatment

was observed and in group 2 a weight loss of 4.4 kg (0.8), 9.7 kg (2.3) 15.1 (3.3) kg was observed at those times. In this study, 96% of patients achieved a loss of more than 5% of body weight at 6 months and 81% lost more than 10% of weight at 12 months [50].

Weight loss associated with dapagliflozin

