6. Use of drugs for weight control.
7. Untreated or uncontrolled hypothyroidism (defined through TSH higher than 4.2 μ U/ml)
8. Pregnant or lactating mother.
9. Tobacco use (in the last month)
10. Current use of steroids or nonsteroidal anti-inflammatory drugs

Withdrawal criteria

1. Becoming pregnant during the study
2. Tobacco use
3. Use of steroids during the study

Sample size

Weight loss after dapagliflozin treatment has not been previously used as primary outcome in randomized controlled trials (RCT) of patients with prediabetes or diabetes and grade III obesity. Zhang et al. performed a meta-analysis that included seven RCTs evaluating the effect of metformin combined with SGLT2-inhibitors (dapagliflozin 10 mg/day, canagliflozin 300 mg/day, empagliflozin 25 mg/day, or ipragliflozin 300 mg/day) vs. metformin (at doses of 1.5 to 3 g/day) with placebo on HbA1c; fasting plasma glucose; and body weight over 24 weeks, 1 year, and 2 years. The total sample was 2847 patients with a mean BMI of 31.7 ± 4.9 kg/m². After a year of treatment, the placebo-metformin control group showed a reduction in body weight of 1.1 ± 3.39 kg, whereas the SGLT-2 inhibitor-metformin group showed a 3.6 ± 4.22 kg reduction with a mean difference of -2.6 kg (-3.17 to -2.03 kg), $p < 0.0000$. Using these data, we calculated a sample size using a mean difference formula. With a power of 80% (alpha level of 0.05) in a two-sided T-test, the sample size required is 90 patients: 45 patients in the M group and 45 patients in the D/M group. The final sample size required is 108 patients: 54 patients in metformin and 54 patients in the dapagliflozin group, allowing for a 20% dropout rate.

Variable definition

Variable name	Variable Type	Scale	Conceptual definition	Operational definition	Units
INDEPENDENT VARIABLES					

Type of treatment	Qualitative, dichotomic	Nominal	Metformin is a biguanide with effect in cyclic AMP kinase that diminishes insulin resistance. Diabetes treatment guidelines consider it as the first line therapy. Dapagliflozin is an SGLT2 inhibitor that induces glycosuria and has been approved for monotherapy in patients with metformin intolerance and also as a second or third line therapy for diabetes.	Use of metformin 2 grams per day or use of metformin 2 grams per day in combination with 10 mg of dapagliflozin.	0 = metformin, 1 = metformin/dapagliflozin
-------------------	-------------------------	---------	--	--	---

DEMOGRAPHIC VARIABLES

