Interleukine 10 (IL-10)	Quantitative continuous	Ratio	Anti-inflammatory cytokine related to the development of atherosclerosis	Concentration determined using the method ELISA.	pg/ml
Ghrelin	Quantitative continuous	Ratio	Hormone secreted in the gastric fundus that induces appetite.	Concentration determined using the method ELISA.	pg/ml

Glucagon	Quantitative continuous	Ratio	Hormone produced by pancreatic alpha cells that counteracts the effects of insulin.	Concentration determined using the method ELISA.	ng/ml
----------	-------------------------	-------	---	--	-------

Statistical analysis: Quantitative variables were described using measures of central tendency and dispersion according to the data distributions. Qualitative variables were described using frequencies or percentages. The Shapiro-Wilk test was used to establish normality in the distribution of quantitative variables. Because information on the different quantitative variables was available up to different time periods, a mixed model analysis was performed using the restricted maximum likelihood (REML) method, as well as a mixed model considering the fixed effects of assigned treatment, sex, and prediabetes or diabetes status, and the random effects of variability in weight loss over time. Comparisons between groups were analyzed using Sidak's post-hoc test. Pearson's chi-square test or Fisher's exact test were used to evaluate the association between qualitative variables. Statistical significance was defined as a $p < 0.05$. Data analysis was performed using SPSS version 17.0 and STATA version 11.0.

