Appendix 2. Collecting data sheet
INSTITUTO MEXICANO DEL SEGURO SOCIAL

Name: _____
 Social security ID number: _____ Treatment
 code _____
 Birthdate: _____ Inclusion date: _____
 Direction: _____
 Phone number: _____ Gender: _____ Height: _____ Age: _____

Relevant history (Cross out the appropriate option)

Smoking (Yes) (No) Age from beginning: _____ Number of years _____

Cigarettes/day: _____

Alcoholism (Yes) (No) Age from beginning: _____ Number of years _____

Drinks/week: _____

Cancer history in family (father, mother, aunt, uncle, grandfather/mother) (Yes) (No)

Type: _____

Comorbidities	Yes	No	Age from diagnosis	Drugs (Frequency/doses)
Hypothyroidism				
Prediabetes				
Diabetes Mellitus				
Hypertension				
Hypertriglyceridemia				
Myocardial infarction/angina				
OSAH syndrome				

Osteoarthritis			

Labs	Initial	Final	Labs	Initial	Final
Glucagon (ng/ml)			Creatinine clearance (ml/min)		
Ghrelin (pg/ml)					
Adiponectin (pg/ml)			iPTH (ng/ml)		
Resistin (ng/ml)			Calcium (mg/dl)		
IL-6 (pg/ml)			Phosphorus (mg/dl)		
IL-10 (pg/ml)			Magnesium (mg/dl)		

Name: _____ NSS: _____

Parameter	1 month	3 months	6 months	12 months
Weight (kg)				
BMI (kg/m ²)				
Waist circumference (cm)				
Systolic blood pressure (mmHg)				
Diastolic blood pressure (mmHg)				
Glucose (mg/dl)				
HbA1c (%)				
TAG (mg/dl)				
TC (mg/dl)				
HDL-c (mg/dl)				
LDL -c(mg/dl)				
Urinary infection (y/n)				
Ketonuria (y/n)				
Proteinuria (y/n)				
Leukocyturia (y/n)				
Nitrite (y/n)				
Sodium (mEq/L)				
Potassium (mEq/L)				

Calcium (mg/dl)				
Phosphorus (mg/dl)				
Magnesium (mg/dl)				
Drugs (hypoglycemic agents, antihypertensives, treatment for dyslipidemia)				

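### The weight model does not adjust for metformin use at entry, although each arm probably mixes patients who start metformin with patients who continue it; the cost is precision, not bias

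*Combined protocol and SAP*

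**What the plan says.** On usual care, section 7 (Prevalence of comorbidities in the Obesity Clinic) says: "At this clinic, patients with prediabetes or T2D are usually treated with metformin 2 g/day". The Abstract also lists metformin as part of the clinic's management of glucose alterations.

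On who enters, the Abstract describes "patients with previous or recently diagnosed diabetes or prediabetes from the Obesity Clinic". The selection criteria in section 8 exclude current insulin or sulfonylurea use. They do not mention metformin, so prior use is neither required, forbidden nor washed out. The one-month run-in comes after assignment in the Workplan and is there to test tolerance.

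On allocation, the Workplan describes computer-generated random numbers and no stratification.

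On analysis, the named fixed effects are those in "a mixed model considering the fixed effects of assigned treatment, sex, and prediabetes or diabetes status". The variable table defines weight as kilograms at baseline and months 3, 6 and 12.

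On data, the Workplan records the type and dose of drugs at baseline, and the comorbidity table in Appendix 2 has a column headed "Drugs (Frequency/doses".

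**The concern.** Both arms receive metformin by assignment. For a patient already taking it, the metformin part of treatment is nothing new; for an untreated patient it is a new drug. If starting metformin lowers weight, the two kinds of patient will have different expected weight changes whichever arm they are in.

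The protocol itself treats metformin as active on weight. Section 7 reports one study in which "they observed a decrease of -2.64 kg of total weight (95% CI -4.23 to -1.05 kg) after one year of treatment", and two others with losses of 2.7 kg at 16 weeks and 3.8 kg at 29 weeks. The hypothesis attributes a 5% loss to metformin alone. A baseline factor that may predict the outcome, and can be derived from data already collected, is therefore left in the residual. Prediabetes/diabetes status is at most a partial stand-in, because the clinic gives metformin in both conditions.

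What is at stake is the width of the interval around the treatment difference, and whether a reader can see how far the result describes adding dapagliflozin to established metformin or starting both together.

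**Working it through.** **Inputs from Sample size, section 8.** "With a power of 80% (alpha level of 0.05) in a two-sided T-test"; "the placebo-metformin control group showed a reduction in body weight of 1.1 ± 3.39 kg"; "the SGLT-2 inhibitor-metformin group showed a 3.6 ± 4.22 kg reduction with a mean difference of -2.6 kg". The plan gives 45 per arm, or 54 per arm after allowing for dropout.

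**Step 1: reproduce the plan's figure.** The raw difference is 3.6 − 1.1 = 2.5 kg. With the larger SD, n = 2 × (1.96 + 0.842)² × 4.22² / 2.5² = 44.7, so 45 per arm; 45 × 1.2 = 54. Exact t-test power at 45 per arm is 0.794 (0.802 by the normal approximation). The figures below use the exact t-test.

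**Step 2: assumptions.** Let p be the share on metformin at entry and g the difference in mean weight change between starters and continuers. The documents give neither. I take p from 10% to 90%. For g I take 1.1 kg (the planning control arm's loss), 2.64 kg and 3.8 kg (the smallest and largest of the three section 7 losses quoted above). None of these was measured as a starter-versus-continuer difference.

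**Step 3: if 4.22 kg excludes the mix.** Leaving the factor out adds p(1 − p)g² to the variance 4.22² = 17.81 kg². Because p(1 − p) is symmetric, 10% and 90% give the same answer and 50% is the worst case. The half-width is 1.96 × SD × √(2/54).

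| g (kg) | p | added variance (kg²) | SD (kg) | power, 45 per arm | 95% half-width, 54 per arm (kg) |
|---|---|---|---|---|---|
| none | – | 0 | 4.22 | 0.794 | 1.59 |
| 1.1 | 10% or 90% | 0.11 | 4.23 | 0.791 | 1.60 |
| 1.1 | 50% | 0.30 | 4.26 | 0.787 | 1.61 |
| 2.64 | 10% or 90% | 0.63 | 4.29 | 0.780 | 1.62 |
| 2.64 | 50% | 1.74 | 4.42 | 0.756 | 1.67 |
| 3.8 | 10% or 90% | 1.30 | 4.37 | 0.765 | 1.65 |
| 3.8 | 50% | 3.61 | 4.63 | 0.717 | 1.75 |

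**Step 4: chance imbalance is already in that half-width.** Imbalance in metformin use between arms shifts the contrast with a 95% range of ±1.96 × g × √(2p(1 − p)/54). For g = 3.8 and p = 50% this is ±0.72 kg. Combined with the within-stratum half-width, √(1.59² + 0.72²) = 1.75 kg, which is the last row of the table. It is one cost seen in two ways, and the two must not be added.

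**Step 5: if 4.22 kg already includes the mix.** Adjustment then removes p(1 − p)g². Power at 45 per arm rises from 0.794 to about 0.80 for g = 1.1 kg, and to between 0.808 (g = 2.64, p = 10%; SD 4.15) and 0.875 (g = 3.8, p = 50%; SD 3.77).

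**Step 6: which term does the adjusting.** If the outcome is kilograms at each visit, the treatment effect is a difference in change over time. A metformin main effect adds the same constant to a patient's baseline and follow-up weights, so it cancels: (y₁₂ + c) − (y₀ + c) = y₁₂ − y₀. With complete data the treatment-by-time estimate is unchanged. Only a metformin-by-visit term acts on change. A main effect is enough when the outcome is change from baseline.

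**The case against.** **Size.** The section 7 losses are within-group changes, and weak evidence of a starting effect. The 2.64 kg figure comes from 25 patients previously on glyburide, whereas current sulfonylurea users are excluded here. The 2.7 kg figure comes from 10 patients measured before and after. The same section introduces this literature as showing modest loss or stability, and the planning control arm lost only 1.1 kg, with prior metformin use there not stated. A reader might infer that starting metformin moves weight by as much as the 2.5 kg under test. The documents do not establish that, and with a 1.1 kg gap the cost is under one point of power. This stands.

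**Bias.** A reader might also infer that the omission biases the treatment comparison. It does not on average, because metformin use at entry is independent of assignment under randomisation.

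**Share.** The proportion on metformin is assumed. If usual care means most are already on it, the loss is at the low end: 0.765–0.780 at 90% for the larger gaps. This stands.

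**Planning SD.** The 4.22 kg is the larger arm's SD and may already include a mix. With the pooled SD, √((3.39² + 4.22²)/2) = 3.83 kg, power is still 0.78 after the largest added variance in the table. So the omission does not show the sample size to be too small.

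**Timing.** The analysis paragraph is in the past tense and the Abstract's period runs to August 2023. Restratifying may be moot, and a term added to the main model afterwards would be post hoc. This shapes the fix but does not remove the point.

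**Conclusion.** The omission is real: a plausible prognostic baseline factor, derivable from data the trial already records, is missing from the weight model and is not described as a stratification factor. That each arm mixes starters and continuers is an inference from usual care, the enrolment description and the silence of the selection criteria; it is probable, but not stated.

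The consequence is lost precision of uncertain size. If 4.22 kg excludes the mix and 10–90% are on metformin at entry, power goes from 0.79 to between about 0.79 (1.1 kg gap) and 0.72 (3.8 kg gap, half on metformin), and the half-width at 54 per arm goes from 1.59 kg to 1.60–1.75 kg. If 4.22 kg includes the mix, the planned power is intact and adjustment only improves it. The adjustment is worth making in either case, provided the term acts on weight change.

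**What to change.** 1. Derive metformin use at entry (yes/no) from the baseline drug record in Appendix 2 and report it by arm with the baseline characteristics.
2. Add it to the weight model: as metformin-by-visit if the outcome is kilograms at each visit, or as a main effect if the outcome is change from baseline. State which outcome is modelled.
3. If the analysis has already been run, keep the existing model as the main result and present the adjusted one as a labelled sensitivity analysis.
4. Stratify the randomisation list on this factor only if recruitment is still open.

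The cost is one model term and one baseline row, with no new visits, no new data and no change in sample size. One limit remains: a yes/no flag treats a recent starter as an established user, and Appendix 2 lists frequency and dose but no start date for each drug.

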6. OBJECTIVES

- a. **Primary objective:** To determine if combined treatment with dapagliflozin and metformin is more effective than monotherapy with metformin for weight loss and assess its effects on waist circumference, triglycerides, blood pressure and inflammatory cytokines in patients with prediabetes and diabetes with obesity class III.
- b. **Secondary objectives:**
 - i. To determine efficacy of metformin monotherapy for weight loss and decrease on waist circumference, triglycerides and blood pressure in patients with prediabetes and diabetes with obesity class III.
 - ii. To compare efficacy of metformin monotherapy and combined treatment with metformin and dapagliflozin.
 - iii. To determine the percentage of patients that with combined treatment achieves a decrease in total weight of 5%, 10% and 15% and the percentage of patients that achieve a decrease in 10% of excess weight.
 - iv. To evaluate if combined treatment allows a decrease in number of drugs needed for comorbidities' control.
 - v. To evaluate prevalence of adverse effects commonly associated with dapagliflozin use (urinary and genital tract infections, hydroelectrolytic alterations) in patients with obesity class III.
 - vi. To determine serum concentration of adiponectin, resistin, IL-6, IL-10 and TNF- α before and after treatments, and compare it between groups.
 - viii. To determine serum concentration of insulin, glucagon and ghrelin before and after treatments, and compare it between groups.

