In a previous study, Bolinder et al. included 182 patients with type 2 diabetes inadequately controlled with metformin (mean HbA1c 7.17%) and evaluated the effect of dapagliflozin 10 mg on total weight after 24 weeks in comparison to placebo. This group found decrease on weight by 2.08 kg (2.8 to 1.31 kg, $p < 0.001$), waist circumference in 1.52 cm (2.74 to 0.31 cm, $p = 0.014$), total fat mass assessed by densitometry (DEXA) in 1.48 kg (2.22 to 0.74, $p = 0.001$), visceral fat mass in 258.4 cm³ (448.1 to 68.6, $p = 0.008$) and subcutaneous fat mass in 184.9 cm³ (359.7 to 10.1, $p = 0.03$) [54].

It is noteworthy that all studies have been conducted in patients with BMI under 40 kg/m², so its effect on weight and other metabolic factors has not been studied in populations with extreme obesity.

Dapagliflozin and inflammatory markers

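### Two mixed models are named and neither is ranked; the only one with listed terms has no fixed visit, treatment-by-visit or baseline-weight term, so its treatment coefficient need not be the one-year difference on which the trial is sized

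*Combined protocol and SAP*

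**What the plan says.** The Statistical analysis paragraph of section 8 is the whole analysis plan. Because follow-up length varies between patients, it says that "a mixed model analysis was performed using the restricted maximum likelihood (REML) method, as well as a mixed model". The first of these comes with no list of terms. The second is given as "considering the fixed effects of assigned treatment, sex, and prediabetes or diabetes status, and the random effects of variability in weight loss over time". Neither is called primary. Between-group comparisons use a Sidak post-hoc test, with no time point or contrast stated.

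The primary objective in section 6 is "To determine if combined treatment with dapagliflozin and metformin is more effective than monotherapy with metformin for weight loss", again with no time point. One year is nonetheless the horizon in three other places in section 8:

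- The Sample size paragraph, which takes its control-arm figure from one-year data ("After a year of treatment, the placebo-metformin control group showed a reduction in body weight of 1.1 ± 3.39 kg") and sets against it a mean loss of 3.6 kg (SD 4.22) on the combination.
- Study Population, which sets one year of clinical assessment per patient.
- Work plan item 11, which acts on weight loss at one-year follow-up.

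The visit lists differ. Work plan item 7 and the Appendix 2 data sheet include month 1. The Abstract and the Weight row of the variable table give months 3, 6 and 12 only. Data stop at the last assessment before surgery, which work plan item 2 places at 3, 6 or 12 months.

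**The concern.** With two unranked models and no named contrast, a reader cannot tell which number answers the primary objective, and the choice could be made after the data are seen.

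The listed model has a further problem. With no fixed visit term and no treatment-by-visit term, it allows one treatment effect common to all visits. If the true difference grows over the year, the coefficient blends early, smaller differences with the month-12 one. How it blends them depends on the random structure, which the wording leaves open: it could be a random intercept, but variability over time reads more naturally as a random slope. What is at stake is the meaning and size of the reported weight effect.

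**Working it through.** **1. The sizing quantity.** Inputs from the Sample size paragraph: arm means 3.6 and 1.1 kg, larger SD 4.22 kg, two-sided 0.05, 80% power.

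- Difference of arm means: 3.6 − 1.1 = 2.5 kg. The paragraph also states a mean difference of 2.6 kg.
- n per arm = 2 × (4.22 × 2.80 / 2.5)² = 44.7, so 45, which is the plan's figure. The t-test power at 45 per arm is 79%.
- With 2.6 kg in place of 2.5 kg, n = 2 × (4.22 × 2.80 / 2.6)² = 41.4, so 42. The stated 45 therefore matches 2.5 kg, which is used below.

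**2. What the listed model estimates.** Assume the response is change from baseline at months 3, 6 and 12 with complete data, and that sex and glycaemic status are balanced by randomisation. With d the vector of true visit differences and V the within-patient covariance, the treatment coefficient has expectation w′d, where w = V⁻¹1 / (1′V⁻¹1). The weights sum to 1. A constant difference is therefore returned unchanged. Otherwise the result depends on V.

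**3. Visit differences used.** Month 6: 2.08 kg, from the 24-week placebo-controlled study in section 7 ("on total weight after 24 weeks in comparison to placebo. This group found decrease on weight by 2.08 kg"). Month 12: 2.5 kg, from step 1. These come from different populations. The documents give no month-3 difference, so it is assumed to lie between 1.04 kg (half of 2.08) and 2.08 kg.

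**4. Random intercept.** The weights are 1/3 each.

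- (1.04 + 2.08 + 2.5) / 3 = 1.87 kg, and 1.87 / 2.5 = 75%.
- (2.08 + 2.08 + 2.5) / 3 = 2.22 kg, and 2.22 / 2.5 = 89%.
- Plateau by month 3: (2.5 + 2.5 + 2.5) / 3 = 2.5 kg.

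**5. Random intercept plus random slope in months, uncorrelated.** V = σ₀²·11′ + σ₁²·tt′ + σₑ²·I with t = (3, 6, 12). All three SDs are assumed.

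| Intercept SD (kg) / slope SD (kg per month) / residual SD (kg) | Weights at months 3 / 6 / 12 | Coefficient, month-3 difference 1.04 kg | Coefficient, month-3 difference 2.08 kg |
|---|---|---|---|
| 1 / 0.35 / 1 | 0.89 / 0.47 / −0.36 | 1.00 kg | 1.93 kg |
| 1 / 0.35 / 2 | 0.71 / 0.43 / −0.14 | 1.29 kg | 2.02 kg |
| 2 / 0.20 / 2 | 0.53 / 0.38 / 0.09 | 1.57 kg | 2.12 kg |

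For example, the top-left value, with weights to three decimals, is 0.892 × 1.04 + 0.473 × 2.08 − 0.364 × 2.5 = 1.00 kg. A slope without a fixed time term makes month 12 the most variable visit, so the model gives it little or negative weight. A plateau by month 3 gives 2.5 kg in every row.

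**The case against.** The unlisted REML model may already be a group-by-visit analysis. The Sidak step suggests several comparisons, and the listed fixed effects have no treatment-by-visit term that could produce them. That is possible, but a model without listed terms cannot be checked, and nothing makes it primary.

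A time-averaged effect is a legitimate target. It is, if stated. The plan does not state it, and sizing and follow-up both point to one year.

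If the response is change from baseline, baseline weight is already used implicitly. This stands in part: the missing baseline covariate is then a matter of precision. It supplies neither a visit term nor a contrast. The calculation above also depends on this reading, since the variable table lists weight in kilograms including baseline, and adding month 1 would change what is averaged.

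The between-arm figures in the Background suggest that the effect flattens: 2.08 kg at 24 weeks, with an interval of 1.31 to 2.8 kg that contains 2.5 kg, and 2.3 kg at 48 weeks when added to pioglitazone. This stands. The gap may be small, and it vanishes under an early plateau.

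A reader might take the Background's 3-, 6- and 12-month losses on metformin as the shape of the treatment difference and infer that the estimate falls to a small fraction of 2.5 kg. Those are uncontrolled total losses in non-diabetic women, not differences between arms, and do not support that. A reader might also infer that few patients will reach month 12 because they leave for surgery. The documents do not settle this: the Background ties candidacy to 10% of excess weight, work plan item 1 to a weight reduction of 10%, and the number remaining depends strongly on which applies.

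**Conclusion.** The point holds as one of specification and estimand. The plan does not say which model is primary, and the only model with listed terms, run as written, in general does not estimate the one-year difference. With the month-12 difference fixed at 2.5 kg, the illustrated coefficient is 1.87 to 2.22 kg under a random intercept and 1.0 to 2.1 kg under the three assumed random-slope settings. It is 2.5 kg if the effect is constant from month 3. These figures rest on an assumed month-3 difference, assumed variances, change scores at three visits and complete data. They show direction and range and do not predict the result.

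Two stronger readings are not supported. It might be inferred that the trial is underpowered: a coefficient nearer zero can come with a smaller standard error, so loss of power is not established, and the 45 per arm is reproducible. It might also be inferred that time is ignored altogether: it is in the random part, and what is missing is a fixed visit term.

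**What to change.** Name one primary model, fitted by REML:

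- Response: change from baseline in weight at each scheduled post-baseline visit.
- Fixed effects: treatment, categorical visit, treatment-by-visit, baseline weight, sex, and prediabetes or diabetes status.
- A stated within-patient covariance; unstructured is one reasonable choice.
- Primary contrast: the treatment difference at month 12.

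Label the other model supportive. If the unlisted REML model already has these terms, list them and name it primary.

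Reconcile the visit lists (with or without month 1) and the two descriptions of surgical candidacy, since the latter determines how many patients have month-12 data. State that the month-12 contrast assumes exits to surgery are explained by observed weight, and report the number of patients observed at each visit by arm.

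This is a cheap improvement: wording and a few more parameters, no new data, possibly a wider interval at month 12. The Statistical analysis paragraph is in the past tense; if the analysis has already been run, present this as a re-analysis.
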